24-months follow-up, End of participation record (for UK reconsented participants only)	X										X

Abbreviations: AE, adverse event; AESI, adverse event of special interest; CRF, case report form; D, Day; eCRF, electronic case report form; eDiary, electronic diary; IRT, interactive response technology; LAR, legally acceptable representative; LRTI, lower respiratory tract infection; MAAE, medically attended adverse event; min, minutes; RSV, respiratory syncytial virus; SAE, serious adverse event; V, Visit

- * D01 is the day of inclusion in the study (ie, verification of inclusion/exclusion criteria, dosing/randomization, access to eDiary, etc.)
- † Electronic reminders to participants' parents or LARs to complete the eDiary in case of an AE or hospitalization. These reminders will be made through the eDiary on a monthly basis until 6 months post-dosing/randomization and at 12 months post-dosing/randomization. It is to be noted that parents or LARs will be able to connect to the eDiary at any time during the first year of the study to report any health events that may occur.
- # Signature of the ICF by parents or LARs can be undertaken before V01. In countries where both parents or LARs are required to provide consent for their infant's participation, signature of the ICF needs to be completed before dosing/randomization and any assessments done at V01. An electronic ICF process can be implemented if applicable as per country regulations.

 Other procedures/assessments such as checking inclusion/exclusion criteria must be performed on D01.

- The Investigator or an authorized designee will provide parents or LARs instructions on how to use the eDiary to report AEs, hospitalizations or any health-related events in their infant, and on how to answer the monthly reminder. The Investigator or an authorized designee will also describe the process through which information on AEs and hospitalization will be collected by the call center.
- From D01 to D366, each time a health event is captured in the eDiary, a medical call center will contact parents or LARs to collect and report the health event's information in the eCRF. The Investigator or an authorized designee will review information reported in the eCRF and interview the participants' parents or LARs if any additional information needs to be collected.

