6.3.2 Blinding and Code-breaking Procedures

Code-breaking procedures are not applicable as this is an open-label study.

Blinding remains a methodological safeguard in clinical trials and is important for limiting bias, such as selection bias, detection bias, and performance bias. In this open-label pragmatic study, nirsevimab immunization will be compared to standard-of-care, ie, no intervention, and having a blinded third party or clinician assessing the patient outcomes is not feasible. Whether the compared groups will receive similar amount of attention cannot be ensured and this, in turn, can result in biased treatment effect estimates with uncertainties on the direction of the bias (underascertainment/over-ascertainment). Methods that decrease risk of bias will be used, such as standardization of questionnaires, a narrowly-defined and objective primary outcome, and when possible electronic health records to retrieve the primary clinical endpoints. Response rates to the questionnaires between the 2 groups will inform about the risk of bias.

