7.3 Lost to Follow-up

A participant will be considered lost to follow-up if her or his parents or LARs cannot be contacted by the site or designee.

The following actions must be taken if the parents or LARs of the participants do not follow-up on the monthly electronic contact (until 6 months after dosing/randomization) or cannot be contacted by phone at the end of the study as planned in the SoA:

- For the monthly electronic contact: the electronic platform will send one reminder for 3 consecutive days. If there is no answer after the e-reminders, the site and/or designee will call the parents or LARs of the participant as soon as possible, discuss the importance of answering the follow-up questions with them, and ascertain whether or not they wish their infant to continue participating in the study.
 - It is to be noted that if both the electronic and phone reminders fail, the next monthly electronic contact (up until 6 months post-dosing/randomization) will take place. The participant will not be deemed lost to follow-up before the 12-months follow-up phone contact for France, Germany, and UK non-reconsented participants or the 24-months follow-up phone contact for UK reconsented participants takes place.
- For the 12 months follow-up phone contact for France, Germany, and UK non-reconsented participants or the 24 months follow-up phone contact for UK reconsented participants, and before a participant is deemed lost to follow-up, the investigator or designee must make every effort to regain contact with the parents or LARs of the participants (where possible, 3 telephone calls and, if necessary, a certified letter to the participant's last known mailing address or local equivalent methods). These contact attempts should be documented in the participant's medical record.
 - Should the parents or LARs continue to be unreachable, the participant will be considered lost to follow-up.

Discontinuation of specific sites or of the study as a whole are handled as part of Appendix 10.1.

8 Study Assessments and Procedures

- Study procedures and their timing are summarized in the SoA. Protocol waivers or exemptions are not allowed.
- Adherence to the study design requirements, including those specified in the SoA, is essential and required for study conduct.

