8.3.9 Health Measurement/Observation

Participants' parents or LARs will be able to report the occurrence of safety events in the eDiary during the first year of the study. In addition, and regardless of whether a safety event was captured during the month, there will be a monthly electronic contact with parents or LARs of the participant, via the eDiary application, to confirm that no health-related events went unreported during the month. The automated monthly electronic contacts will occur up to 6 months post-dosing/randomization. If parents or LARs of the participant confirm that a safety event occurred during the past month, a phone investigations by the site staff and/or designee will be triggered, and the data will be recorded in the eCRF.

At 12 months, a safety follow-up phone call will be made to the parents or LARs of the participant by the site personnel or designee.

Parents or LARs of UK reconsented participants will be able to report any hospitalizations and emergency room visits that occurred from D366 to D731 post-dosing/randomization in the memory aid.

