5.1. Time Points and Visit Windows

5.1.1. General Definitions

All assessment days will be related to Day 1. Day 1 is the date of randomization (for no intervention group) / immunization (for nirsevimab group).

Relative days after Day 1 are calculated as (assessment date – Day 1 date) + 1. Relative days prior to Day 1 are calculated as (assessment date – Day 1 date). The day prior to Day 1 is Day -1. Day 0 is not defined.

The date of the immunization for each participant in the nirsevimab group will be taken from the Immunization eCRF page. If the date on this eCRF page is missing, alternatively the date of randomization will be used.

The date of the randomization for each participant in the no intervention group will be taken from the Randomization eCRF page. If the date in this eCRF page is missing, alternatively the date of informed consent (Informed Consent Date eCFR page) will be used.

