5.1.4. Analysis Windows for monthly reporting of events via eDiary

[Table 5 Definition of Analysis Windows for monthly reporting of events of interest via eDiary](#) describes and provides the relative study day ranges to be applied to the date of event reporting by parents via eDiary to derive the analysis windows for monthly reporting of events of interest.

The following considerations are to be followed when deriving the analysis windows:

- The relative day number of the event reporting lies between the lower and upper boundary of the window (the boundary values are included)

Table 5 Definition of Analysis Windows for monthly reporting of events of interest via eDiary

	Analysis Window ^a
Month 1	Day 1 to 31
Month 2	Day 32 to 61
Month 3	Day 62 to 91
Month 4	Day 92 to 121
Month 5	Day 122 to 151
Month 6	Day 152 to 181
Month 7	Day 182 to 211
Month 8	Day 212 to 241
Month 9	Day 242 to 271
Month 10	Day 272 to 301
Month 11	Day 302 to 331
Month 12	Day 332 to 366 +14 days (From Day 332 to 380)
Month 18	Day 367 +14 to 546 +14 (From Day 381 to 560)
Month 24	Day 547 +14 to 745 (From Day 561 to 745)

^a Relative to randomization (for no intervention group) / immunization (for nirsevimab group)

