6.6.7.8. Follow-up

Number and percentage of participants will be provided for:

- Monthly responses in eDiary according to the analysis window in Section 5.1.4.

In addition, at the time of First Year Analysis, follow-up time in months will be described for all participants (based on the primary endpoint RSV LRTI Hospitalizations), participants with RSV LRTI Hospitalizations, participants with Very Severe RSV LRTI, participants with Hospitalizations for all-cause LRTI at the following timeframes (see Section 6.1 for details on the descriptive statistics):

- Through the RSV Season (overall and in each country)
- Through Day 151 post-dosing/randomization (overall and in each country)
- Through Day 181 post-dosing/randomization (overall and in each country)
- From 181 days post-dosing/randomization to 366 days post-dosing/randomization in participants with no event before Day 181 (overall and in each country, excluding participants with very severe RSV LRTI)

Follow-up time in months will also be summarized at the time of Second Year analysis:

- From 366 days post-dosing/randomization to 731 days post-dosing/randomization in UK reconsented participants. However, this will not be summarized for subgroup of participants with Very Severe RSV LRTI.
- From 366 days post-dosing/randomization to 511 days post-dosing/randomization in UK reconsented participants. However, this will not be summarized for subgroup of participants with Very Severe RSV LRTI.
- From 512 days post-dosing/randomization to 731 days post-dosing/randomization in UK reconsented participants. However, this will not be summarized for subgroup of participants with Very Severe RSV LRTI.
- Through Day 511 post-dosing/randomization in UK reconsented participants. However, this will not be summarized for subgroup of participants with Very Severe RSV LRTI.
- Through Day 731 post-dosing/randomization in UK reconsented participants. However, this will not be summarized for subgroup of participants with Very Severe RSV LRTI.
- Through Day 366 post-dosing/randomization in UK reconsented participants (recurrent wheeze event)
- From Day 366 post-dosing/randomization to Day 731 post-dosing/randomization in UK reconsented participants (recurrent wheeze event)
- Through Day 731 post-dosing/randomization in UK reconsented participants (recurrent wheeze event)

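### SAP Table 5 closes Months 1 to 6 on the day each eDiary reminder falls due, so late answers count in the next month and monthly response rates may mislead

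*SAP*

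**What the plan says.** **Contact schedule.** The Schedule of Activities (Protocol 1.3) places electronic contacts at D31, D61, D91, D121, D151 and D181. A window of +14 days is printed once for that block. On frequency it says: "These reminders will be made through the eDiary on a monthly basis until 6 months post-dosing/randomization and at 12 months post-dosing/randomization". Protocol 8.3.9 gives the purpose of the monthly contact: "to confirm that no health-related events went unreported during the month". If a contact is not answered, Protocol 7.3 states that "the electronic platform will send one reminder for 3 consecutive days", after which the family is telephoned.

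**Windows.** SAP 5.1.4 assigns entries by reporting date; its Table 5 holds the "relative study day ranges to be applied to the date of event reporting by parents via eDiary to derive the analysis windows". Month 1 is Day 1 to 31, Month 2 is Day 32 to 61, and so on to Month 6, Day 152 to 181. Month 7 is Day 182 to 211. Month 12 is given as "Day 332 to 366 +14 days (From Day 332 to 380"). Months 18 and 24 also carry the 14 days.

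**Use.** SAP 6.6.7.8 asks for the number and percentage of participants for "Monthly responses in eDiary according to the analysis window in Section 5.1.4". Protocol 6.3.2, on the limits of the open-label design, says: "Response rates to the questionnaires between the 2 groups will inform about the risk of bias".

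**The concern.** Each of the first six contacts asks about the month that is ending, and each window shuts on the day the question is put. A family that answers the next day, while reminders are still being sent, is recorded as silent for the month in question and as responding in the month after. The resulting percentages mix two things: whether families answer, and how fast.

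That would be a small matter of labelling if the table were only a log of entries. It matters more because the protocol gives between-group response rates a role in judging bias in an open-label trial with an untreated control arm, and the SAP plans no other summary of eDiary response. If families in one arm answer more slowly, the table can show a difference in response where none exists. If they answer equally slowly, it can understate a difference that does exist.

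**Working it through.** **1. Day numbering and the plan's own figures.** SAP 5.1.1 sets the scale: "Relative days after Day 1 are calculated as (assessment date – Day 1 date) + 1". V01 + 180 days is therefore D181. The windows that carry the allowance reproduce exactly: 366 + 14 = 380 (end of Month 12); 367 + 14 = 381 and 546 + 14 = 560 (Month 18); 547 + 14 = 561 and 731 + 14 = 745 (Month 24).

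**2. Where an answer falls.** Each contact has 15 permitted days, D to D+14, if the +14 days applies to every contact.

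| Contact | Permitted days | Window closing that month | Permitted days inside it | Later days fall in |
|---|---|---|---|---|
| D31 | 31–45 | Month 1 (1–31) | 1 of 15 | Month 2 |
| D61 | 61–75 | Month 2 (32–61) | 1 of 15 | Month 3 |
| D91 | 91–105 | Month 3 (62–91) | 1 of 15 | Month 4 |
| D121 | 121–135 | Month 4 (92–121) | 1 of 15 | Month 5 |
| D151 | 151–165 | Month 5 (122–151) | 1 of 15 | Month 6 |
| D181 | 181–195 | Month 6 (152–181) | 1 of 15 | Month 7 |
| D366 | 366–380 | Month 12 (332–380) | 15 of 15 | none |

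The reminder run alone gives the same result on a shorter scale. If its three days start on the contact day, days two and three (D32 and D33 for the first contact) already belong to the next month.

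**3. Effect on the percentages.** The documents give neither a response rate nor a late share, so both are assumed. Let R be the true response to each contact and L the share of answers that come late. Assume one answer per contact, no spontaneous entries, and response and lateness independent from month to month. Then:

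- Month 1 shows R(1 − L).
- Months 2 to 6 each show 1 − [1 − R(1 − L)] × [1 − RL].
- Month 7 shows RL.

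With R = 80%:

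| L | Month 1 | Months 2–6 | Month 7 |
|---|---|---|---|
| 10% | 72.0% | 1 − 0.28 × 0.92 = 74.2% | 8.0% |
| 30% | 56.0% | 1 − 0.44 × 0.76 = 66.6% | 24.0% |
| 50% | 40.0% | 1 − 0.60 × 0.60 = 64.0% | 40.0% |

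**4. Between arms, under the same assumptions.**

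- Equal R and equal L: no gap in any month.
- R = 80% in both arms, L = 10% against 30%: a false gap of 72.0 − 56.0 = 16.0 points in Month 1, 7.7 points in Months 2 to 6 (74.24 − 66.56), and 8.0 − 24.0 = −16.0 points in Month 7.
- True gap of 85% against 75%, L = 30% in both arms: Month 1 shows 59.5 − 52.5 = 7.0 points and Months 2 to 6 show 69.8 − 63.2 = 6.6 points, in place of 10.

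**5. If lateness is a stable habit.** Suppose the same share L of families is always late, with the same R as the rest. In Months 2 to 6 the prompt families are credited from the current contact and the late ones from the previous contact, so each month shows (1 − L)R + LR = R. The Months 2 to 6 gap of 7.7 points then becomes 0. Months 1 and 7 are distorted exactly as before.

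**The case against.** The case on the other side has real weight.

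- **Table 5 is worded for event reports.** Parents may make entries at any time in the first year, so consecutive windows by reporting date are a legitimate description. This stands. The windows fail only when the counts are read as response to each contact.
- **Answers are shifted, not lost, and the rule is the same in both arms.** A false gap needs lateness to differ by arm, and the documents give no evidence that it does. This stands, but it is not a full defence: equal lateness can still shrink a true gap.
- **The +14 days is printed once, beside V01 + 180 days.** It may apply only to D181. The D181 spill into Month 7 holds on either reading, and the three-day reminder run carries the point to every month, though over fewer days.
- **The later months are tied to telephone contacts.** This explains Months 18 and 24, where a memory aid replaces the eDiary. Month 12 has an eDiary reminder of its own, so the contrast with Months 1 to 6 remains.
- **The SAP does not call the 6.6.7.8 table a bias check.** Nor does that line say it is by arm. The link to Protocol 6.3.2 is an inference, and the SAP separately plans a tipping-point analysis (6.6.2.2) and a time-to-discontinuation analysis (6.6.7.5).

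A reader might infer that the response table is simply wrong, or that the trial's assessment of bias or its efficacy result is compromised. The documents do not support that. Only SAP 6.6.7.8 refers to Section 5.1.4. Efficacy events come from medical records, and the censoring rules in SAP 6.6.1 do not use these windows.

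**Conclusion.** The point holds in a limited form. For Months 1 to 6, only the contact day itself falls in the month being asked about; any later answer is credited to the next month, and late answers to the D181 contact appear in a month with no reminder. The table therefore does not measure response to each contact, and may mislead if used for the comparison in Protocol 6.3.2. The day arithmetic is certain for D181 and for the later reminder days; the full 14-day spill at every contact depends on how the Schedule of Activities is read.

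The size is not known. The 16.0 and 7.7 points are illustrations that rest on assumed response and late shares, and the 7.7 also on independence from month to month. The consequence is confined to one descriptive table; no efficacy or safety analysis is affected.

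**What to change.** Carry the 14 days into the first six windows of Table 5, as is already done for Month 12:

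- Month 1: Day 1–45
- Month 2: Day 46–75
- Month 3: Day 76–105
- Month 4: Day 106–135
- Month 5: Day 136–165
- Month 6: Day 166–195
- Month 7: from Day 196

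These windows do not overlap, and each holds all 15 permitted days of its own contact. Alternatively, if reminder dates are available in the database (the documents do not show that they are), link each answer to the reminder it answers. Either way, state in SAP 6.6.7.8 that the table is by arm, and show the share answered after the contact day.

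The re-windowing costs one edited table and one derivation, and needs only the reporting day already in use. It has a small downside: a spontaneous entry made in the 14 days after a reminder is credited to the earlier month. Show spontaneous entries separately where they can be identified.

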5.2. Handling of Dropouts, Missing Data, and Outliers

5.2.1. Handling of Missing Efficacy Data

Efficacy data (ie, LRTI hospitalization) will be collected through the participants' medical records and reported in the eCRF by the site personnel or designee. Efficacy data will be analyzed accounting for the follow-up time post-dosing/randomization up to the data cut-off date.

For the participants who do not have the efficacy endpoints of interest at the time of the Primary Analysis, the end date for the efficacy follow-up will be the end of the RSV season, or the last available date with confirmation of no such efficacy endpoints, or the cut-off date of the Primary Analysis, whichever occurs first. The efficacy follow-up will be censored at the end date.

For the participants who do not have the efficacy endpoints of interest through the RSV season at the time of the First Year Analysis, the end date for the efficacy follow-up will be the last available date with confirmation of no such efficacy endpoints or the end of RSV season whichever is earlier. The efficacy follow-up will be censored at the end date.

For the participants who do not have RSV LRTI hospitalization through Day 151/ Day 181 post-dosing/randomization, from 181 days post-dosing/randomization to 366 days post-dosing/randomization or from 366 days post-dosing/randomization to 731 days post-dosing/randomization, please refer to sections 6.6.4.3.2, 6.6.4.3.4, 6.6.4.3.5 and 6.6.4.3.6. For participants who do not have recurrent wheeze events through Day 366/ Day 731 post-dosing/randomization, please refer to section 6.6.4.3.7.

5.2.2. Handling of Missing Safety Data

Adverse event imputations for missing severity or relationship are given in Section 6.7.2.1. Unknown or partial medication and AE date imputations are given below and are to be used only for the assessment of prior / concomitant status for medications and treatment-emergent status for AEs.

5.2.3. Handling of Partial and Missing Dates for Date of Birth, Adverse Events, Prior / Concomitant Medications / LRTI Hospitalizations/ Recurrent Wheeze Events

5.2.3.1. Partial and Missing Dates of Birth

Age is a stratification factor for randomization and would not be missing. The missing Date of Birth will not be imputed if age is available. In rare cases, both age and Date of Birth are missing, the following convention will be used:

Where the day is missing and month and year are available the day will be completed as the 15th. For example, Date of Birth specified as --JAN1980 will be completed as 15JAN1980.

If the day and month are missing and the year is available, the day and month will be completed as 02JUL (the 183rd day of the year). For example, Date of Birth specified as ----1980 will be completed as 02JUL1980.

The imputed Date of Birth will be compared to the date of Informed Consent Form (ICF) or randomization to ensure consistency. The Date of Birth should be set to the earlier date of ICF and randomization if imputed Date of Birth is after the date of ICF or randomization.

5.2.3.2. Missing or Partial Dates for Adverse Event and Prior / Concomitant Medication

Missing and / or incomplete dates for medications and AEs are imputed in a manner resulting in the earliest onset or the longest duration during the Treatment Period, whilst ensuring that

the start date does not occur after the stop date. The stop date will not be imputed if the medication or AE is “Ongoing”. Technically, this will be done as follows:

For a missing / incomplete start date the earliest date of the following will be imputed:

- The later date of: the earliest possible start date, and the date of the randomization (for no intervention group) / immunization (for nirsevimab group)
- The latest possible start date
- The latest possible stop date

For a missing / incomplete stop date the latest date of the following will be imputed:

- The earlier date of the latest possible stop date and the date of last dose of treatment
- The earliest possible stop date
- The earliest possible start date

Here, the earliest possible date is defined as:

- The date itself if available
- The date of the first day of the month, if month and year are available but the day is missing
- The date of the first day of the year, if year is available but day and month are missing
- The day of informed consent, if the date is completely missing

The latest possible date is defined as:

- The date itself if available
- The date of the last day of the month, if month and year are available but the day is missing
- The date of the last day of the year, if year is available but day and month are missing
- The date of last known date on the study for the participant plus one year, if the date is completely missing

